19.2.3. the line is	Rate of blood/CSF culture sampling per 1000 PICC-days over total time in situ	
19.2.4.	Type of organism grown (clinically serious BSI)	34
19.2.5.	Type of organism grown (from BSI excluding arterial or CVC samples).	34

				•	•	•	•	•	-	pathogenic 34
1 20.	Safety E	valuation	s				 			35 35
	20.2.	Presenta	tion	of the dat	a	•••••	 			35
21. 22. 23.	Appendi	ces					 			36 36 37
	23.2.	Appendix	c II				 			38

5. Statement of Compliance

This Statistical Analysis Plan (SAP) provides a detailed and comprehensive description of the

pre-planned final analyses for the study " $\underline{\mathsf{PREV}}$ enting infection using $\underline{\mathsf{A}}$ ntimicrobial

Impregnated Long lines (PREVAIL)". The planned statistical analyses described within this

document are compliant with those specified in brief within the PREVAIL protocol version 5.0.

This study is carried out in accordance with the World Medical Association Declaration of

Helsinki (1964) and the Tokyo (1975), Venice (1983), Hong Kong (1989) and South Africa

(1996) amendments and will be conducted in compliance with the protocol, Clinical Trials

Research Centre (CTRC) Clinical Trials Unit (CTU) Standard Operating Procedures (SOPs)

and EU Directive 2001/20/EC, transposed into UK law as the UK Statutory Instrument 2004

No 1031: Medicines for Human Use (Clinical Trials) Regulations 2004.

These planned analyses will be performed by the trial statistician. The results of the final

analysis described within this statistical analysis plan will be contained within a statistical

analysis report. This report will be used as the basis of the primary research publications

according to the study publication plan.

All analyses are performed with standard statistical software (SAS version 9.3 or later). The

finalised analysis datasets, programs and outputs will be archived following Good Clinical

Practice guidelines and SOP TM021 Archiving procedure in CTRC. The testing and validation

of the statistical analysis programs will be performed following SOP ST001.

6. Background and Rationale

The rationale for the trial is outlined in the protocol. To summarise, currently antibiotic

impregnated central venous catheters are used in paediatric and adult intensive care.

However, no neonatal units (NNUs) in the UK use antimicrobial impregnated coated

peripherally inserted central catheters (AM-PICCs) (despite the AM-PICCs being CE marked).

When surveyed, neonatologists cite the lack of randomised controlled trial (RCT) evidence in

preterm babies as an important reason for the lack of adoption of impregnated lines in the UK

(unpublished). The trial is needed now because potential health gains are unlikely to be

realised without robust evidence from a RCT. Clear evidence is needed of the effectiveness

of AM-PICC on blood stream infection (BSI), the safety of AM-PICC, particularly on antibiotic

resistance, and the cost-effectiveness, to enable neonatologists to decide about whether or

not to adopt these devices in NNUs.

7. PREVAIL Study Objectives

The primary objective of this trial is to determine the effectiveness of antimicrobial impregnated

(with rifampicin and miconazole) peripherally inserted central catheter (AM-PICC) compared

with standard peripherally inserted central catheter (S-PICC) for reducing BSI.

The null hypothesis is that there is no difference in time to BSI based on any positive blood

culture (including fungal isolates) taken between 24 hours after randomisation until 48 hours

after PICC removal between the intervention (AM-PICC) group and the control (S-PICC)

group. The alternative hypothesis is that there is a difference between the two groups.

The secondary objectives of this trial are to determine the effect of AM-PICC vs S-PICC on

the secondary outcomes listed in section 9.2

8. Investigational Plan and Study Design

8.1. Overall study design and plan- description

This trial is an open label, 2-arm randomised controlled trial to determine the effectiveness

and cost effectiveness of antimicrobial impregnated (with rifampicin and miconazole) long

lines (AM-PICC) compared with standard long lines (S-PICC) for reducing blood stream

infection (BSI).

8.2. Treatments studied

A PICC is a very narrow tube placed through the skin and into a central vein to allow

medicines, fluids or parenteral nutrition to be given into one of the large veins near to the heart.

The control treatment in PREVAIL is an S-PICC, which is an un-impregnated PICC. The

intervention treatment is an AM-PICC, which is an antimicrobial impregnated PICC. Further

details on the trial treatments can be found in sections 2.1 and 7.2 of the study protocol.

8.3. Description of treatment adherence

If a baby has their PICC removed less than 24 hours after insertion then this is classed as

non-adherence to treatment. Babies who receive a PICC other than the randomised PICC will

be reported in the CONSORT flow diagram (see section 14).

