8.4. Patient population studied

The trial population aims to include 858 babies who require the narrowest PICC (Premicath 1

French gauge (Fr)).

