8.8. Sequence and duration of all study periods

A schematic of the study design can be found in section 1 of the study protocol. A table of trial

assessments can be found in section 8.1 of the protocol.

To summarise this information, the researcher (clinician or research nurse) will approach

parents of eligible babies to discuss PREVAIL and to obtain consent. Once consent is

obtained, the baby will then be randomised to either AM-PICC or S-PICC. Consent is valid for

14 days. If the baby has not been randomised within 14 days, the parents will need to

reconsent. Babies are followed up clinically and for safety until 48 hours after removal or

attempted insertion (if attempted but not inserted) or randomisation (if randomised but not

inserted). There is a retrospective review of key events at discharge home from neonatal care,

death or 26 weeks post randomisation, whichever occurs first and at all transfers to other

hospitals.

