17.3. Presentation of data for treatment adherence

Tables mentioned within this section will be presented overall and split by treatment.

Frequency tables (with percentages) will be presented for:

Reasons for PICC removal

• The number of babies whose PICC was removed less than 24 hours after

randomisation

The number of babies receiving the allocated PICC

The number of babies receiving a non-allocated PICC

The number of babies randomised but did not receive any PICC

The type of sample and whether an e-test was performed for positive cultures

• Length of time PICC is in situ for (from insertion to removal).

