17.4.1.2. Analysis

The following will be reported overall and split by sample type and treatment:

• Number of babies with sample taken in primary outcome time window (24 hours after

randomisation and up to 48 hours after PICC removal)

Number of samples taken in primary outcome time window

Number of babies with BSI in the POTW

This is a time to event outcome and will be analysed using the log-rank test and Kaplan-Meier

curves presented with the numbers at risk for each treatment group. The median and

interquartile range for time to BSI will be presented.

Cox proportional hazard regression models will be used if appropriate. However, since the

hazard of infection may not be constant post CVC insertion, non-proportional hazards survival

models will also be investigated. Results will be presented using Hazard Ratios and 95%

confidence intervals, along with the log-rank p-value.

Differences between date and time of randomisation and date and time of insertion will be

summarised using medians and IQR.

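### Non-adherence is defined by PICC removal within 24 hours of insertion, but the adherence tables count from randomisation, so the tabulated count can equal or understate the defined one

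*SAP*

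**What the plan says.** SAP section 8.3 gives the plan's only timing definition of non-adherence: "If a baby has their PICC removed less than 24 hours after insertion then this is classed as" non-adherence. The clock starts at insertion.

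Section 17.3, headed "Presentation of data for treatment adherence", lists the tables to be shown overall and by arm. Its one row with a 24-hour limit is "The number of babies whose PICC was removed less than 24 hours after" randomisation. The same list contains "Length of time PICC is in situ for (from insertion to removal", which runs on the insertion clock but states no cut-off. The other rows cover reasons for removal, whether the allocated line, another line or no line was received, and sample type and e-tests.

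On the order of events, section 8.8 says that once consent is "obtained, the baby will then be randomised to either AM-PICC or S-PICC. Consent is valid for" a limited period. It also provides for babies who are randomised but have no line inserted. Section 17.4.1.2 treats the interval between the two events as something to report: "Differences between date and time of randomisation and date and time of insertion will be" summarised by median and IQR. No value for that interval appears in the SAP.

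**The concern.** The plan defines one quantity in 8.3 and tabulates another in the section meant to present adherence. A programmer who follows 17.3 literally produces a count that is not the one 8.3 describes, and nothing would flag it: the independent programming in section 21 covers the primary analysis only.

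Adherence figures tell the reader how much exposure to the allocated line lies behind the intention-to-treat comparison. If the 17.3 row is read as the number of non-adherent babies under 8.3, it may leave out some babies whose line was in place for less than a day.

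**Working it through.** The SAP states no figure on this point, so there is nothing to reproduce. The check is one of logic, followed by an illustration on stated assumptions.

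**Logic.** For a baby with a line inserted, let g be the hours from randomisation to insertion (g ≥ 0, from the order of events in 8.8) and d the hours from insertion to removal.

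- Section 8.3 counts babies with d < 24.
- The 17.3 row counts babies with g + d < 24.
- Since g ≥ 0, g + d < 24 implies d < 24. Every baby in the 17.3 row is therefore non-adherent under 8.3.
- The converse fails for babies with 24 − g ≤ d < 24. These are the ones missed.
- If g is 24 hours or more, that baby cannot appear in the 17.3 row however short the dwell.

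**Size, even spread.** If early removals are spread evenly over the first 24 hours of dwell and every baby has the same gap g, the missed share is g/24: 1/24 = 4%, 3/24 = 12.5%, 6/24 = 25%, 12/24 = 50%.

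**Size, constant hazard.** Let q be the share of babies whose line is removed within 24 hours of insertion. The hourly removal hazard is λ = −ln(1 − q)/24, and the share that the 17.3 row captures is p = 1 − exp(−λ(24 − g)). The undercount is (q − p)/q.

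Inputs:
- N = 858, the target in section 8.4 ("The trial population aims to include 858 babies who require the narrowest PICC (Premicath 1" French gauge line), treated for illustration as if every baby had a line inserted.
- q = 5%, assumed.
- g from 0 to 24 hours, assumed.

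The defined count is 858 × 0.05 = 42.9. With λ = 0.0513/24 = 0.00214 per hour:

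| Assumed gap g (h) | Count in the 17.3 row | Undercount | Chance that at least one baby is missed |
|---|---|---|---|
| 0 | 42.9 | 0% | 0 |
| 1 | 41.2 | 4% | 0.83 |
| 3 | 37.7 | 12% | over 0.99 |
| 6 | 32.4 | 25% | over 0.99 |
| 12 | 21.7 | 49% | over 0.99 |
| 24 | 0 | 100% | over 0.99 |

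The percentage undercount hardly changes with q: at 6 hours it is 25% for q = 2% and 24% for q = 10%. The number of babies does change. At q = 2% the defined count is 17.2, a 1-hour gap gives a row of 16.5, and the chance of missing at least one baby is 0.51.

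With the row counted from insertion, the undercount is zero by construction.

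**The case against.** Four points can fairly be made for the plan.

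- *The row is correctly described.* It says that it counts from randomisation and does not call itself non-adherence. A reader is misled only by equating it with 8.3. That stands, but the row sits under the adherence heading, it is the only 24-hour row there, and the quantity that 8.3 defines is tabulated nowhere.
- *The origin may be deliberate.* The primary outcome window opens 24 hours after randomisation, and PICC-days in the window are counted from that moment (17.5.4.1). The row may be meant to show lines already out by then. This is plausible, though the SAP does not say so. It supports keeping the row under its own label, but does not supply the missing count.
- *The time-in-situ row carries the information.* It uses the insertion clock and is shown by arm. The 8.3 count could be read from it if a category boundary fell at 24 hours. The plan specifies no such boundary, so this is possible but not assured.
- *The gap may be short.* Section 14.1 lists, among reasons for consent without randomisation, the need for a different size of line and the lack of trained staff or of the device. This hints that randomisation takes place close to insertion. It is inference only, but nothing in the SAP supports a gap of 6 or 12 hours either.

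A reader might infer that reported non-adherence is bound to be too low. The documents do not support that: the two counts agree if no line is removed between 24 hours from randomisation and 24 hours from insertion. Nor do they support a bias between arms, since the row is defined identically in both and nothing indicates that the gap differs by arm.

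**Conclusion.** The inconsistency is real. Sections 8.3 and 17.3 use different starting points for the same 24-hour limit, and the adherence tables contain no row for non-adherence as defined. The direction follows from the order of events alone: the tabulated count is equal to the defined count or lower.

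The size cannot be fixed from the SAP, which gives neither the gap nor the early-removal rate. About g/24 of early removals would be missed, assuming an even spread and a common gap; for a gap of an hour or so that is about 4%. The larger percentages in the table show how the shortfall grows with the gap and are not estimates for this trial.

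The consequence is limited to descriptive reporting. A reader might suppose that the efficacy result is touched. It is not: efficacy is analysed by intention to treat (17.1), the safety set is defined by insertion or attempted insertion (20.1), and no per-protocol set uses the 8.3 definition. No estimate, test or analysis population changes. This is a minor correction, worth making because it is simple.

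**What to change.** In section 17.3, add or substitute a row counting babies whose PICC was removed within 24 hours of insertion, labelled as non-adherence per section 8.3. If the randomisation-based row is kept to show removals before the primary outcome window opens, give it its own label saying so.

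The cost is one line of SAP text and one derived variable. Date and time of insertion are already needed for 17.4.1.2 and 19.1.2, and date and time of removal are recorded on Form 6 (17.4.1.1), so no new data are required.

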8.4. Patient population studied

The trial population aims to include 858 babies who require the narrowest PICC (Premicath 1

French gauge (Fr)).

8.4.1. Inclusion criteria

The inclusion criteria can be found in section 5.1 of the protocol.

8.4.2. Exclusion criteria

The exclusion criteria can be found in section 5.2 of the protocol.

8.4.3. Removal of patients from therapy or assessment

All babies will have their PICC removed at some point. Case report form (CRF) "Form 6:

Removal" records the reason for PICC removal. These include:

PICC no longer needed

Removed because of confirmed infection

Removed because of suspected infection

Damaged

Unintended removal

PICC blocked

Thrombosis

Clinically evident thrombophlebitis

Pre-specified duration of use reached

Malposition identified during x-ray

Babies will be observed for clinical follow-up for 48 hours after the PICC removal and a

retrospective review of key events will take place when the baby is discharged

home/dies/reached 26 weeks post randomisation, unless the parent/legal representative

instructs otherwise.

8.5. Consent process

Consent is sought from the parent or legal representative for those babies who are likely to

require a PICC.

Once written consent has been provided by the parent or legal representative it is valid for 14

days. If the baby has not been randomised within the 14 days the research nurse (RN) or

clinician will need to reconsent the parent/legal representative of the baby. Further details can

be found in sections 6.2 and 11.3 of the protocol.

8.6. Blinding

This is an open-label trial because AM-PICCs can be distinguished from S-PICCs as rifampicin

causes brown staining on the tubing. No details on blinding will be presented.

8.7. Method of assignment to treatment

Full details of the randomisation procedure can be found in sections 6.3 and 9.2 of the protocol.

The randomisation list will be generated by a statistician (who is not involved with the PREVAIL

trial) at the CTU. Babies will be randomised to AM-PICC or S-PICC in a ratio of 1:1.

Randomisation will be stratified by centre. Babies will be randomised using a secure (24-hour)

web based randomisation programme controlled centrally by the CTU to ensure allocation

concealment. Details of block sizes can be found in the Statistics Trial File under section 4.

8.8. Sequence and duration of all study periods

A schematic of the study design can be found in section 1 of the study protocol. A table of trial

assessments can be found in section 8.1 of the protocol.

To summarise this information, the researcher (clinician or research nurse) will approach

parents of eligible babies to discuss PREVAIL and to obtain consent. Once consent is

obtained, the baby will then be randomised to either AM-PICC or S-PICC. Consent is valid for

14 days. If the baby has not been randomised within 14 days, the parents will need to

reconsent. Babies are followed up clinically and for safety until 48 hours after removal or

attempted insertion (if attempted but not inserted) or randomisation (if randomised but not

inserted). There is a retrospective review of key events at discharge home from neonatal care,

death or 26 weeks post randomisation, whichever occurs first and at all transfers to other

hospitals.

8.9. Schedule of assessments

A full schedule of trial assessments and timeline of data collection can be found in section 8.1

of the protocol.

9. Listing of Outcomes

9.1. Primary outcome

The primary outcome is time to BSI based on any positive blood/CSF culture (any positive

bacterial or fungal blood/CSF culture will be included) taken between 24 hours after

randomisation until 48 hours after PICC removal.

9.2. Secondary outcomes

Outcomes captured up until 48 hours after PICC removal:

1. Rifampicin resistance in any isolate from blood/CSF culture.

2. Rifampicin resistance in any isolate from PICC tips.

3. Type of organism isolated from BSI.

4. Rate of BSI per 1000 PICC-days (including recurrent BSI).

5. Occurrence of 1 or more BSI.

6. Rate of catheter-related BSI per 1000 PICC days.

7. Rate of blood/CSF culture sampling per 1000 PICC days.

8. Duration of antimicrobial exposure from randomisation up to 48 hours after PICC

removal.

9. Time to PICC removal.

Outcomes captured up until discharge home from neonatal care/death/6 months post

randomisation:

10. Chronic lung disease 36 weeks postmenstrual age.

11. Necrotizing enterocolitis (NEC): Bell's stage II or III.

12. Treatment for retinopathy of prematurity.

13. Abnormalities on cranial ultrasound.

14. Time to full milk feeds after randomisation.

15. Total duration of parenteral nutrition from randomisation until discharge from NNU.

16. Death:

a) within 6 months (26 weeks) of randomisation

b) before discharge home from neonatal care

c) time to death

10. Determination of Sample Size

The sample size calculation can be found in section 9.4 of the protocol.

11. Study Framework

The overall objective for each of the study outcomes (primary and secondary) is to test the

superiority of AM-PICCs compared with S-PICCs.

12. Confidence Intervals, p-values and Multiplicity

All applicable statistical tests will be two-sided and will be performed using a 5% significance

level; confidence intervals presented will be 95%. No adjustment will be made for multiplicity

for the secondary outcomes. Percentages will be presented as 1 decimal place. Test statistics,

p-values, confidence intervals and measures of spread will be presented as 2 decimal places.

13. Timing and Objectives of Interim and Final Analyses

13.1. Interim monitoring and analyses

Details on interim analyses are compatible with those found in the protocol in section 9.5. The

IDSMC will meet annually unless members have specific concerns that would require the

meetings to be held more frequently as stated within section 5.3 of the IDSMC Charter.

There will be a formal interim analysis of the primary outcome half-way through the trial (when

approximately half of the participants have been randomised), using Peto-Heybittle stopping

rules. At this point the IDSMC will make a recommendation to the Trial Steering Committee

(TSC) for the trial to continue or stop. Statistical significance alone will not stop the trial; a

decision to discontinue recruitment will be made only if the result is likely to convince a broad

range of clinicians including parents of babies in the trial and the general clinical community

or if there are safety issues. The IDSMC will also review the parameters used within the

sample size calculation at this time. See "Statistical Analysis Plan for IDSMC reports" for

details on the information presented to the IDSMC.

13.2. Final analysis

The final analysis for all outcomes will be analysed after the end of the trial, which is defined

in section 8.6 of the protocol as "the date on which data for all participants is frozen and data

entry privileges are withdrawn from the trial database."

14. Disposition of Participants

14.1. Screening, eligibility and recruitment

If the parents/legal representative has been approached for consent, the baby will be recorded

on "Log A: Screening Log" and details of whether they went on to be randomised will also be

recorded here.

If a baby's parent/legal guardian was not approached for consent but later went on to receive

a PICC, they will be recorded on "Log B: Missed patient log".

Screening logs will be summarised by site in a table detailing:

- i) the number of babies whose parents/legal representatives were approached for consent.
- ii) the number of babies whose parents/legal representatives were not approached for consent (missed babies),
- iii) those who provided consent, (expressed as a frequency and a % with the denominator being i),
- iv) those who were randomised (expressed as a frequency and a % with the denominator being iii),

Reasons for not being approached will be summarised in a table with the following categories:

- Parents not available to consent
- Parents lack of understanding
- Parents don't understand English/Urdu
- Consultant preference
- Missed by clinical team
- Baby previously entered into PREVAIL
- Not approached for other reason

Frequencies will be presented along with percentages using the denominator as ii).

Reasons for consent declined will be summarised in a table with the following categories:

- No reason provided.
- Parent doesn't want to take part in research.
- Parent doesn't wish baby to be randomly assigned to treatment.
- Parent doesn't wish baby to have antimicrobial PICC.
- Other reason.

Frequencies will be presented along with percentages using the denominator as iii).

Reasons for consent provided but not randomised will be summarised in a table with the following categories:

- Baby requires different size PICC
- Baby no longer requires a PICC
- Baby died
- Trial trained staff not available
- Unable to access randomisation system
- PICC (Premicath 1Fr) not available

Other reason

Frequencies will be presented along with percentages using the denominator as iv).

A recruitment summary table will be presented showing the following for each centre: centre code, hospital name, dates site opened/closed to recruitment, dates of first/last randomisation

and total number randomised.

The following details will be summarised in a CONSORT flow diagram (appendix A):

the number of babies whose parents were approached for consent

the number of babies whose parents were not approached for consent

• the number of babies whose parents were approached but didn't go on to be

randomised

those babies who were randomised

those who received the randomised allocation

• those who did not receive the randomised allocation

those who withdrew from the study after randomisation

those who were lost to follow-up

the number of babies included in primary analysis

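### Two descriptive screening tables in SAP section 14.1 cite denominators that exclude the babies they describe

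*SAP*

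**What the plan says.** SAP section 14.1 (Screening, eligibility and recruitment) sets out a by-site screening summary with four numbered counts:

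- Item i) counts the babies for whom consent was sought.
- Item ii) counts the missed babies, for whom no approach was made.
- Item iii) covers "those who provided consent, (expressed as a frequency and a % with the denominator being i".
- Item iv) counts the babies that went on to randomisation, shown also as a percentage of iii).

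Three tables of reasons follow, each with its own denominator:

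- Reasons for not being approached: "Frequencies will be presented along with percentages using the denominator as ii".
- Reasons for declining consent: "Frequencies will be presented along with percentages using the denominator as iii".
- Reasons why consented babies were not randomised: "Frequencies will be presented along with percentages using the denominator as iv".

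Nothing elsewhere in the SAP amends these three rules.

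**The concern.** The first table divides by the group whose reasons it lists. The second and third do not. A family that declined cannot be counted in iii), and a consented baby that was not randomised cannot be counted in iv). The printed percentage is therefore so many decliners per 100 consenters, or so many non-randomised per 100 randomised, in a column that readers will take as a share of a whole.

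The practical harm is misreading. The decline table has a category for parents who did not want the antimicrobial PICC. As specified, its percentage depends on the overall consent rate as well as on how common that reason is among decliners, so two sites with the same mix of reasons but different consent rates would show different percentages. A programmer who follows the text literally will produce these figures. Section 21 (Quality Control) specifies independent programming for the primary analysis only, so it should not be relied on to catch the slip.

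**Working it through.** The SAP states no figure for these tables, so there is none to reproduce. The check matches each numerator to its denominator and then sizes the effect.

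**Numerator against denominator (section 14.1)**

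| Table of reasons | Babies in numerator | Denominator cited | Numerator inside denominator? |
|---|---|---|---|
| Not approached | not approached | ii) not approached | yes |
| Consent declined | declined | iii) consented | no |
| Consented, not randomised | consented, not randomised | iv) randomised | no |

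**Inputs**

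- Target number randomised: 858 (section 8.4), used only to scale the illustration.
- c = iii/i, the share of those approached who consent: not in the SAP, assumed.
- r = iv/iii, the share of those consenting who are randomised: not in the SAP, assumed.
- Everyone approached who did not consent is counted as declining: assumed.

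**Column totals as written**

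- Decline table: (i − iii)/iii = (1 − c)/c.
- Not-randomised table: (iii − iv)/iv = (1 − r)/r.

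| Assumed share (c or r) | Total as written | Total over the group described | Total over the preceding stage |
|---|---|---|---|
| 0.4 | 0.6/0.4 = 150% | 100% | 60% |
| 0.5 | 0.5/0.5 = 100% | 100% | 50% |
| 0.6 | 0.4/0.6 = 66.7% | 100% | 40% |
| 0.8 | 0.2/0.8 = 25% | 100% | 20% |
| 0.9 | 0.1/0.9 = 11.1% | 100% | 10% |

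The total passes 100% only when the share is below 0.5. At exactly 0.5 it equals 100% by coincidence.

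**Illustration in counts, with c = 0.6 and r = 0.8 assumed**

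- Consented: 858/0.8 = 1,072.5. Approached: 1,072.5/0.6 = 1,787.5.
- Declined: 1,787.5 − 1,072.5 = 715. As written, 715/1,072.5 = 66.7%. Over the approached, 715/1,787.5 = 40%.
- Consented, not randomised: 1,072.5 − 858 = 214.5. As written, 214.5/858 = 25%. Over the consented, 214.5/1,072.5 = 20%.

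**Single rows.** If a share s of decliners give one particular reason, the row prints s(1 − c)/c. The intended figure is s (share of decliners) or s(1 − c) (share of those approached). The printed value equals s only at c = 0.5, and for any non-zero row it exceeds s(1 − c) whenever c is below 1.

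**The case against.** The strongest reply is that little depends on this. The tables are descriptive recruitment summaries that feed no outcome, analysis set or test. Frequencies are printed beside the percentages, so a reader can recompute the right figure. All rows of a table share one denominator, so the ranking and relative size of the reasons are preserved. The number of parents refusing the antimicrobial PICC is reported correctly either way. All of this stands, and it keeps the point minor.

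A reader might infer more than the SAP supports in four ways:

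- **That the percentages are meaningless.** They are mislabelled ratios, but the counts beside them keep the tables usable.
- **That totals above 100% are to be expected.** This needs fewer than half of approached families to consent, or fewer than half of consented babies to be randomised. The SAP gives neither rate.
- **That these tables are the plan's evidence on representativeness, or are certain to be published.** The SAP says neither. Section 5 sends results to a statistical analysis report that forms the basis of publications. Section 14.1 also gives approached, consented and randomised figures with coherent denominators.
- **That only one correction is possible.** Dividing by the group described follows the not-approached table. Dividing by the preceding stage follows the SAP's own percentages for iii) over i) and iv) over iii). Both are coherent.

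What the reply does not remove is that the two rules as written follow neither convention.

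**Conclusion.** The point holds as a definite but minor error: two of the three reason tables in section 14.1 cite a denominator disjoint from the numerator. The mismatch rests on the SAP's wording alone and needs no assumption. Its size does: totals of (1 − c)/c and (1 − r)/r depend on consent and randomisation shares that the SAP does not give, and on counting every non-consenter as a decliner. Over the assumed range 0.4 to 0.9 the totals run from 150% down to 11.1%. Counts, the CONSORT flow (which lists numbers only), the analysis sets and every treatment comparison are unaffected.

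**What to change.** Correct the two denominator sentences in section 14.1 and state one convention for both tables:

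- **Group described, matching the not-approached table.** Divide reasons for declining by the number recorded as declining consent, and reasons for non-randomisation by iii) minus iv). Each table then totals 100% if one reason is recorded per baby. Name the decliners directly instead of writing i) minus iii), because the two agree only if every approached family that did not consent is recorded as declining.
- **Preceding stage, matching items iii) and iv).** Divide reasons for declining by i) and reasons for non-randomisation by iii). The tables then total 1 − c and 1 − r, and a footnote should say so.

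The cost is two edited sentences in the SAP and a small change to the table program. No new data are needed, except that the first option needs the declined count, which the decline table already requires.
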